5.0 STUDY DESIGN

5.1 STUDY DESCRIPTION

This study is a multi-center, open-label, randomized clinical trial conducted at Duke Cancer Institute and Indiana University to evaluate whether incisional NPWT can help reduce the rate of SSI in patients undergoing either colorectal or hepatopancreatobiliary surgery. Up to 170 subjects will be randomized in a 1:1 ratio to either conventional wound care (control group) or the incisional NPWT (experimental group) to ensure 138 evaluable subjects.

The primary study endpoint will be SSI within the laparotomy wound, as assessed on postoperative day 4-5 and the first postoperative clinic visit, which is anticipated to be within 30 days of surgery. Evaluable subjects are defined as those who have been randomized and completed both postoperative assessments. Non-evaluable subjects are those subjects who were randomized but did not complete both post-op visits. Non-evaluable scenarios include aborted surgeries, cancelled surgeries, death unrelated to study, and early device removal related to device malfunction. Screen failures are defined as those subjects not randomized.

Safety endpoints will be adverse events related to the device or dressing, including the presence of any abnormal skin findings (such as blisters or rash). These endpoints will be assessed from the day of surgery through the 30-day follow-up visit.

Subjects randomized to conventional wound care (control group) will have their skin incisions closed with skin staples, sutures, or surgical glue (per judgment of the treating physician), covered with sterile medical gauze and a form of adherent (tape or clear adhesive) for which the subject does not have any allergy. This dressing will be removed per the treating physician's discretion or institutional standards.

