10.1 STATISTICAL ANALYSIS

The primary analysis will include all randomized and evaluable patients but exclude ineligible patients or patients who are canceled from the study before receiving any wound care. SSI is defined as an infection that occurs within 30 days of operation. The primary endpoint is the SSI rate. The primary analysis of comparing the conventional wound care (control group) and the incisional V.A.C® (experimental group) will be conducted using a chi-square test for two-sample binomial probabilities with a one-sided significance level of 0.1. The observed SSI rates and 90% Upper Confidence Bound (UCB) estimates will be reported. Preoperative, intraoperative, and postoperative variables will be tabulated and appropriate summary statistics will be reported. As a secondary analysis, comparison of treatment groups for SSI will be adjusted for any significant preoperative, intraoperative, or postoperative variables using logistic regression.

For secondary endpoints, the incidence of SSI as superficial incisional, deep incisional, and organ/space will be estimated along with the 90% UCBs. The secondary endpoint length of stay is a continuous variable. A Wilcoxon rank sum test will be used to assess the significance of the difference between groups in median length of stay. Median length of stay, its range and quartiles will be reported.

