12.0 SAFETY REPORTING REQUIREMENTS

12.1 DEFINITIONS

The definitions in this section have been adapted from the Code of Federal Regulations (CFR) and the International Conference on Harmonization (ICH) Guidelines for Good Clinical Practices (GCPs). Please refer to the complete regulations and guidelines for additional details regarding these definitions. This study will only evaluate adverse events that are probably or possibly related to the NPWT units and dressings (e.g. blistering, redness, etc).

Adverse Event (AE) [ICH GCP]: An Adverse Event (AE) shall mean any untoward medical occurrence. For the purposes of this study, only adverse events thought to be related to the dressing will be collected and recorded.

Unanticipated adverse device effects [21 CFR 812.150]: Any serious adverse effect on health or safety, any life-threatening problem or death caused by, or associated with a device, if that effect, problem or death was not previously identified in nature, severity, or degree of incidence in the application; or any other unanticipated serious problem associated with a device that relates to the rights, safety, or welfare of subjects. An investigator shall submit to the sponsor and to the reviewing IRB a report of any unanticipated adverse device effect occurring during an investigation as soon as possible, but in no event later than 10 working days after the investigator first learns of the effect.

Deviations from the investigational plan [21 CFR 812.150]: An investigator shall notify the sponsor and the reviewing IRB of any deviation from the investigational plan to protect the life or physical well-being of a subject in an emergency. Such notice shall be given as soon as possible, but in no event later than 5 working days after the emergency occurred. Except in such an emergency, prior approval by the sponsor is required for changes in or deviations from a plan, and if these changes or deviations may affect the scientific soundness of the plan or the rights, safety or welfare of human subject, FDA and IRB approval is also required.

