12.2 PROCEDURES FOR REPORTING

All adverse events deemed possibly or probably related to the NPWT unit and dressings that are identified from the time of placement of the NPWT or standard of care wound application through 30 days post-surgery should be recorded on the CRFs.

Serious Adverse Events (SAEs) must ALSO be reported within 2 business days of learning of an event. The DCI Safety SAE Review Form must be completed and promptly submitted to the funding company. The forms should include at minimum the following information but should not be held until all information is available. The funding source, KCI, will be notified using the KCI USA, Inc. SAE Report Form. The Duke study team will send SAE Report Form to KCI USA, Inc. within 2 business days of knowledge of the SAE. External sites should report SAEs to the Duke study team within 24 hours. Reporting instructions for external sites can be found in the REDCap study eManual. The Duke study team will be responsible for reporting to the supporting company as well as the Duke IRB and/or FDA, where applicable. In accordance with applicable regulations, Investigators must report SAEs to their local IRB according to their institutional guidelines.

Additional information and/or corrections may be submitted as they are obtained. All SAEs must be followed through resolution or stabilization.

The initial report for each SAE should include at minimum the following information:

- protocol # and title
- patient initials, study identification number, sex, age
- date the event occurred
- description of the SAE
- description of the patient's condition
- indication whether the patient remains on study
- causality or causal relationship

SAEs should be reported by fax to the following:

KCI USA, INC
[contact]
Email: [contact]

Events will be reviewed and reported to the Duke IRB according to local IRB guidelines.

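### Section 5.1 leaves study-related deaths unclassified, and its plain definition drops a patient whose SSI was documented before death

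*Combined protocol and SAP*

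**What the plan says.** Section 5.1 defines the two groups by visit completion alone: "Evaluable subjects are defined as those who have been randomized and completed both postoperative assessments", and "Non-evaluable subjects are those subjects who were randomized but did not complete both post-op visits". Neither sentence asks why a visit was missed.

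The next sentence gives examples: "Non-evaluable scenarios include aborted surgeries, cancelled surgeries, death unrelated to study, and early device removal related to device malfunction". Death is the only entry qualified by its relation to the study.

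Section 10.1 builds the primary analysis on that definition: "The primary analysis will include all randomized and evaluable patients". It also leaves out ineligible patients and those who came off the study with no wound care given. It does not mention death. It counts an infection as an SSI if it arises in the 30 days after the operation.

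Other relevant places:
- Section 9.0 lists death as a reason for discontinuation, with no causal qualifier and no analysis rule.
- Sections 7.3.3 and 7.3.4 let either postoperative assessment be done by reviewing clinical data. The second visit is at day 30, plus or minus 14 days.
- Section 5.1 describes the design: "This study is a multi-center, open-label, randomized clinical trial conducted at Duke Cancer Institute and Indiana University".
- Section 12.1 limits safety evaluation: "This study will only evaluate adverse events that are probably or possibly related to the NPWT units and dressings". Section 12.2 records such events "from the time of placement of the NPWT or standard of care wound application through 30 days post-surgery".

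No section defines a death as related or unrelated to the study, names who decides, or says how a related death is scored.

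**The concern.** Two problems follow.

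The first is ambiguity. The completion rule covers every death before the second visit, but the list names only some deaths. A reader can take the qualifier as idle, or as meaning that related deaths are handled in some other way. If related deaths stay in the analysis, no outcome is assigned to them. The choice between these readings could be made by people who know the arm and the patient's course.

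The second arises even when the text is read in the simplest way. If every early death is non-evaluable, an SSI already seen at day 4-5 is discarded when the patient later dies. The exclusion then removes an observed primary event for a reason that comes after randomisation. With few events expected, one or two such patients could matter.

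**Working it through.** **1. Does the list do more than illustrate the definition?**
- It is introduced as open-ended, which favours reading it as examples only.
- Removal of the device for malfunction does not stop a patient from attending both visits, yet it is listed as non-evaluable. At least one entry therefore excludes by cause and not by missed visit, so the qualifier on death cannot safely be called idle.
- Because an assessment may be done from records, it is also not fixed whether the second assessment of a patient who has died could be completed from the chart.

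The text permits more than one rule for a study-related death and does not choose between them.

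**2. Does the plain definition discard endpoint events?** Take an SSI documented on day 5 and a death on day 12.
- Section 10.1 endpoint: infection within the 30-day period, so it qualifies.
- Section 5.1: second visit not completed, so non-evaluable.
- Section 10.1 analysis set: evaluable patients only, so the patient and the event are both removed.

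**3. The plan's own figure.** Inputs from Sections 5.1 and 10.0: 17% v 5%, one-sided 0.1, 138 evaluable (69 per arm).
- SE under the null = √(2 × 0.11 × 0.89 / 69) = 0.0533
- SE under the alternative = √((0.17 × 0.83 + 0.05 × 0.95) / 69) = 0.0523
- Power = Φ((0.12 − 1.2816 × 0.0533) / 0.0523) = Φ(0.99) = 83.9%; exact enumeration gives 86.3%.

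The stated value of about 85% is reproduced. If deaths in both arms are excluded, exact power is 85.9% to 85.1% for assumed mortality of 1% to 5%. Power is not the issue.

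**4. Illustrative effect on the result.** At the observed overall rate of 11% (Section 10.0), 138 × 0.11 = 15.2 events. Assumed 30-day mortality of 1% to 3% would give 170 × 0.01 = 1.7 to 170 × 0.03 = 5.1 deaths; the documents give no rate. The test is z = (a/n₁ − b/n₂) / √(p̄(1 − p̄)(1/n₁ + 1/n₂)), where p̄ = (a + b)/(n₁ + n₂).

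| Control v NPWT | Change | z | one-sided p |
|---|---|---|---|
| 10/69 v 5/69 | assumed start, 15 events | 1.367 | 0.086 |
| 9/68 v 5/69 | one infected control death dropped | 1.157 | 0.124 |
| 8/67 v 5/69 | two dropped | 0.931 | 0.176 |
| 10/69 v 4/68 | one infected NPWT death dropped instead | 1.664 | 0.048 |
| 12/69 v 3/69 | near design rates (69 × 0.17 = 11.7; 69 × 0.05 = 3.5) | 2.461 | 0.007 |
| 10/67 v 3/69 | two infected control deaths dropped | 2.098 | 0.018 |

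**5. Deaths without an SSI.** From an assumed 11/69 v 5/69 (p = 0.055):
- excluding one to four NPWT patients who died without SSI gives p = 0.059 to 0.071;
- keeping them as no SSI leaves p = 0.055;
- counting one as an SSI gives p = 0.098, and two gives p = 0.156.

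Excluding such patients changes little. What matters is a lost event, or how a death is scored.

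**The case against.** The strongest reply is that the definition already settles the matter. Both defining sentences in Section 5.1 are free of any causal condition, the list only gives examples, and Sections 9.0 and 10.1 add no relatedness test. A reader might infer from the qualifier that a death removes a patient only when it is judged unrelated. The documents do not support that: naming one kind of death as an example does not make the other kind evaluable.

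A reader might also infer that the rule works differently by arm, since a death is more easily attributed to a suction device than to gauze. That is conjecture. No section handles deaths by arm, adverse-event recording starts at placement of either dressing, and Section 3.0 states that no extra risks are known for either form of care. If nearly all deaths in both arms are called unrelated, the qualifier treats the arms alike.

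The numerical illustration is also limited. It starts from a borderline result and puts the infected deaths in one arm. A neutral rule that excluded all deaths would produce the same shift. Losing control events also works against NPWT, so that case cannot create a false claim of benefit.

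These replies dispose of the two stronger readings. They do not supply a rule for related deaths, and they do not answer the loss of an SSI documented before death, which follows from the plain definition itself.

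**Conclusion.** The point holds as a gap in the definition of the primary analysis set. Section 5.1 does not settle how a study-related death is classified, and the qualifier invites an undefined judgement in an open-label trial. Read plainly, Sections 5.1 and 10.1 together remove patients whose SSI was documented before death, contrary to the 30-day endpoint.

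A difference between arms is possible but not shown, and the direction of any bias depends on where such deaths fall. The effect is small unless the result is close: one infected death can carry an assumed 10/69 v 5/69 across the 0.10 threshold, while two do not change the conclusion at 12/69 v 3/69. This rests on assumed event counts and on one or two patients dying after a documented SSI. The documents give no number of deaths.

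**What to change.** In Sections 5.1 and 10.1:
- Delete the relatedness qualifier. Deleting it alone would make every death an exclusion, so also state that death after wound care has been applied does not make a patient non-evaluable.
- Apply one rule to all deaths within 30 days after wound care is applied, whatever the cause. The patient stays in the randomised arm and in the denominator; an SSI documented before death counts as an event; without one the patient counts as no SSI.
- Add a sensitivity analysis in which each such death counts as an event.
- Report deaths by arm. Section 9.0 already has the reason for discontinuation recorded, but no section commits to this table.

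The cost is a sentence in each section, one extra analysis and one table. Scoring a death without SSI as no event is a simplification, because the patient was not observed for the full period; the sensitivity analysis covers this. Section 10.0 reports that the study endpoint had not been analysed at the time of the amendment, so the rule should be fixed before any comparison by arm.

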Subjects randomized to the incisional NPWT (experimental group) will have their skin incisions closed with skin staples or sutures (per judgment of the treating physician), a layer of non-adhesive dressing (Adaptic: Johnson & Johnson, New Brunswick, New Jersey) will cover the skin staples or sutures, followed by placement of an adhesive (Benzoin: generic), a Prevena™ Incision Management System peel and place or customizable dressing (KCI USA, Inc, San Antonio, Texas) covering only the skin staples or sutures. Please note, surgical glue should not be used for the experimental group. NPWT will be delivered using either the Prevena pump or the ActiV.AC. The incisional NPWT will then be continued for a minimum of 2 days up to a maximum of 7 days depending on physician preference.

Subjects will be clinically managed according to routine standard of care. Subjects will be assessed during their inpatient stay and at the time of routine postoperative clinic visits which is anticipated to be within 30 days of discharge. Presence or absence of SSI will be determined on postoperative day 4-5 and again at the time of the postoperative clinic visit, which is anticipated to be within 30 days of discharge. Criteria for determination of SSI are listed in Section 8.

Patients who are candidates for a laparoscopic approach will not be recruited. Note: patients scheduled for a staging laparoscopy followed by an open procedure are permitted to participate.

See Appendix 1 for the study schema.

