7.3.4 Post-op Visit Day 30 (+/-14)

- Post-operative incision assessment
- Review of any side effects or symptoms
- This may be conducted by a review of clinical data

- PI will confirm the clinical data of any finding indicative of infection (i.e. redness, fever, positive culture)

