8.0 CLASSIFICATION OF SSI BY NSQIP

The following definitions will be used to classify SSI:

Superficial Incisional SSI: Superficial incisional SSI is an infection that occurs within 30 days after the operation *and* infection involves only skin or subcutaneous tissue of the incision *and* at least *one* of the following:

- Purulent drainage, with or without laboratory confirmation, from the superficial incision.
- Organisms isolated from an aseptically obtained culture of fluid or tissue from the superficial incision.
- At least one of the following signs or symptoms of infection: pain or tenderness, localized swelling, redness, or heat AND superficial incision is deliberately opened by the surgeon, unless incision is culture-negative.
- Diagnosis of superficial incisional SSI by the surgeon or attending physician

Deep Incisional SSI: Deep Incision SSI is an infection that occurs within 30 days after the operation and the infection appears to be related to the operation and infection involved deep soft tissues (for example, fascial and muscle layers) of the incision and at least one of the following:

- Purulent drainage from the deep incision but not from the organ/space component of the surgical site.
- A deep incision spontaneously dehisces or is deliberately opened by a surgeon when the patient has at least one of the following signs or symptoms: fever ($> 38^{\circ}$ C), localized pain, or tenderness, unless site is culture-negative.
- An abscess or other evidence of infection involving the deep incision is found on direct examination, during reoperation, or by histopathologic or radiologic examination.
- Diagnosis of a deep incision SSI by a surgeon or attending physician.
- Report infection that involves both superficial and deep incision sites as deep incisional SSI.

Organ/Space SSI: Organ/Space SSI is an infection that occurs within 30 days after the operation and the infection appears to be related to the operation *and* the infection involves any part of the anatomy (for example, organs or spaces), other than the incision, which was opened or manipulated during an operation *and* at least *one* of the following:

- Purulent drainage from a drain that is placed through a stab wound into the organ/space.
- Organisms isolated from an aseptically obtained culture of fluid or tissue in the organ/space.

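### The second SSI assessment has conflicting time anchors, and none guarantees that SSI status is known through day 30 from surgery, the window that defines the primary endpoint

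*Combined protocol and SAP*

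**What the plan says.** All places are in the combined protocol and SAP.

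- **When SSI is assessed.** Section 5.1: "Presence or absence of SSI will be determined on postoperative day 4-5 and again at the time of the postoperative clinic visit". Section 4.1 names the same two occasions and gives the clinic visit no time limit.
- **Anchor for the clinic visit.** Where Section 5.1 introduces the primary endpoint, it describes "the first postoperative clinic visit, which is anticipated to be within 30 days of surgery". Further on in the same section, the assessment takes place "again at the time of the postoperative clinic visit, which is anticipated to be within 30 days of discharge"; the discharge wording appears twice there.
- **Visit window.** The study calendar (Section 7.1) and the heading of Section 7.3.4 give a third version, "Post-op Visit Day 30 (+/-14" days).
- **Event definition.** Section 10.1: "SSI is defined as an infection that occurs within 30 days of operation". Section 8 agrees: "Superficial incisional SSI is an infection that occurs within 30 days after the operation", with the same limit for deep incisional and organ/space SSI. The second Section 5.1 description refers the reader to Section 8 for the criteria.
- **Who is analysed.** Under Section 5.1 a randomized subject who has had both postoperative assessments is evaluable, whatever the day of the second.
- **How it is assessed.** Sections 7.3.3 and 7.3.4 list an incision assessment, a review of side effects or symptoms, permission to work from clinical data, and PI confirmation of findings that suggest infection. Neither mentions an onset date or says that the second assessment must cover the period up to day 30.

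**The concern.** The endpoint is a cumulative 30-day incidence counted from the operation. To measure it, each evaluable subject's status must be known from surgery through day 30, and an infection discovered later must be dated. The plan fixes the event definition but ties detection to a visit that can fall well before or well after day 30, described in three ways.

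There are two consequences. A subject seen early leaves the last part of the window unobserved and still enters the denominator as infection-free. A subject seen late may have an infection whose place relative to day 30 has to be worked out afterwards, with no rule for doing so, in an open-label trial. Either way the measured rate need not be the 30-day rate that Section 10.1 defines and Section 10 powers the trial for.

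**Working it through.** **Step 1. Put the timing statements on one scale, days from surgery.**

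| Source | Second assessment | Earliest | Latest |
|---|---|---|---|
| Section 5.1, endpoint paragraph | within 30 days of surgery | no limit given | day 30 |
| Section 5.1, later paragraph | within 30 days of discharge | no limit given | day 30 + length of stay |
| Sections 7.1 and 7.3.4 | day 30 ± 14 | 30 − 14 = day 16 | 30 + 14 = day 44 |
| Sections 8 and 10.1 (event window) | – | day of operation | day 30 |

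The documents give no length of stay. For assumed stays of 7 and 14 days, the discharge wording allows a visit as late as 7 + 30 = day 37 or 14 + 30 = day 44.

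**Step 2. Compare visit and event window.** A visit on day 16 meets the calendar and makes the subject evaluable. It leaves 30 − 16 = 14 days of the event window with no SSI assessment specified. Adverse-event recording under Section 12.2 does run to 30 days after surgery, but it is confined to events related to the NPWT unit and dressings, so it does not fill the gap. A visit on days 31 to 44 covers the whole window, but an infection first seen then counts only if its onset was by day 30, and the listed assessments do not ask for that date.

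**Step 3. Reproduce the plan's power.** Inputs from Section 10: 17% versus 5%, one-sided α = 0.10 (z = 1.2816). From Section 5.1: 138 evaluable, so n = 69 per arm. With p̄ the mean of the two rates and no continuity correction,

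power = Φ{[(p₁ − p₂) − 1.2816·√(2p̄(1 − p̄)/n)] / √([p₁(1 − p₁) + p₂(1 − p₂)]/n)}.

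At n = 69: (0.12 − 1.2816 × 0.0533)/0.0523 = 0.989, so power = 83.9%. With 170 × 0.86 = 146 evaluable, or 73 per arm, it is 85.4%. Both agree with the stated figure of approximately 85%.

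**Step 4. Illustrate the effect of early visits.** Assumption: a fraction f of 30-day SSIs is missed, the same in both arms, with 69 per arm. Both rates are multiplied by (1 − f).

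| f | Control | NPWT | Difference | Power |
|---|---|---|---|---|
| 0 | 17.0% | 5.0% | 12.0 points | 83.9% |
| 5% | 16.15% | 4.75% | 11.4 points | 82.2% |
| 10% | 15.3% | 4.5% | 10.8 points | 80.4% |
| 20% | 13.6% | 4.0% | 9.6 points | 76.4% |
| 30% | 11.9% | 3.5% | 8.4 points | 71.8% |

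The planned event count is 69 × 0.17 + 69 × 0.05 = 15.2, so f = 10% is about 1.5 missed events and f = 20% about 3. The documents do not give the distribution of visit days, so f itself cannot be estimated.

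**Step 5. How much can one event matter?** Pooled z test, 69 per arm, one-sided:

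| Control v NPWT events | p |
|---|---|
| 10 v 5 | 0.086 |
| 9 v 5 | 0.130 |
| 10 v 6 | 0.144 |
| 12 v 3 | 0.007 |
| 11 v 3 | 0.012 |
| 12 v 4 | 0.017 |

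One reclassified event changes the decision at 10 v 5, a split chosen to lie near the 0.10 boundary. Near the planned effect (12 v 3) it does not.

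**The case against.** The strongest defence is that the event definition never varies. Sections 8 and 10.1 both stop at 30 days from operation, and the discharge-anchored text itself points to Section 8. This stands. A reader might infer from the discharge wording that infections starting after day 30 can be counted; the documents do not support that, because a late visit does not widen the event window.

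A reader might also infer that observation time differs by arm, since length of stay is a secondary endpoint and the discharge anchor moves with it. That is not supported either. The visit is only anticipated by a certain time, the calendar window is the same for both arms, time after day 30 adds nothing to the event window, and the documents give no length-of-stay data by arm.

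Nor does it follow that an infection treated and healed between visits is lost. Several Section 8 criteria are past events (an opened incision, a culture, a diagnosis), and Sections 7.3.3 and 7.3.4 allow clinical data to be reviewed.

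Finally, the CRF is not among the documents, so an onset date may be collected in practice. That limits the point to what the plan asks for. It does not answer the early-visit problem: a record review done on day 16 cannot see days 17 to 30, and nothing requires a second look.

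**Conclusion.** The point holds as a mismatch between ascertainment and endpoint. The anchors conflict within Section 5.1 and with the calendar, and none of the versions secures SSI status through day 30 for every evaluable subject. The better-supported risk is under-counting after early visits. For late visits, the weakness is that applying the 30-day limit depends on a date that the listed assessments do not request.

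The size depends on how many visits fell before day 30 and how many infections followed them, which the documents do not show. If 10% to 20% of SSIs were missed equally in both arms, at 69 per arm, power would be about 80% to 76% instead of about 84%, and the reported rates would understate the 30-day incidence by the same proportion. The one-event example is a boundary case and does not show that the trial's conclusion is fragile. The correction should be made before the primary analysis because it concerns how the primary endpoint is measured.

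**What to change.** 1. Reconcile Sections 4.1, 5.1 and 7.1 to one anchor, days from surgery, and carry it into Section 7.3.4. Remove the discharge-based timing.
2. State that the second assessment establishes SSI status over the whole interval from surgery through day 30, including infections diagnosed and treated between visits. If the clinic visit is earlier than day 30, complete the assessment at or after day 30 by the clinical-data review that Section 7.3.4 already allows.
3. Record the date of onset of every SSI.
4. State in Section 10.1 that an SSI enters the primary endpoint only if onset is on or before day 30, whatever the day of the visit.

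Cost: wording, one CRF date, and a short record review for subjects seen before day 30. Section 10 reports 143 subjects already enrolled out of a maximum of 170, so much of this would be done from existing charts; it should be finished before the arms are compared. The event definition, test and sample size stay as they are.
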